3.2.2 Secondary Outcome Measures

The **Secondary Safety Endpoints** to be used to evaluate the safety of this study are:

- The occurrence of vaccine-related serious adverse events (SAE) from the first vaccination through 6 months after the last dose of vaccine is administered

The **Secondary Immunogenicity Endpoints** to be used to evaluate the immune response to vaccination will consist of the following:

- At any time after vaccination, the proportion of participants with a ≥ 4 -fold rise in dmLT-specific serum IgG and IgA titers over baseline measured by ELISA
- At any time after vaccination the proportion of participants with > 8 dmLT-specific IgA or IgG ASC / 10^6 PBMC as measured by ELISpot
- At any time after vaccination, the proportion of participants with ≥ 2 -fold rise in ALS anti-dmLT-specific IgG and IgA titers over baseline measured by ELISA
- At any time after vaccination, the proportion of participants with a ≥ 4 -fold rise over baseline in dmLT-specific fecal IgA titers measured by ELISA
- At any time after vaccination, the proportion of participants with a ≥ 4 -fold rise over baseline in dmLT-specific salivary IgA titers measured by ELISA

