##### 3.2.2. Secondary Outcome Measures

The **Secondary Safety Endpoints** to be used to evaluate the safety of this study are:

- The occurrence of vaccine-related serious adverse events (SAE) from the first vaccination through 6 months after the last dose of vaccine was administered
-

The **Secondary Immunogenicity Endpoints** to be used to evaluate the immune response to vaccination consist of the following:

- At any time after vaccination, the proportion of participants with a  $\geq 4$ -fold rise in dmLT-specific serum IgG and IgA titers over baseline measured by Enzyme-Linked Immunosorbent Assay (ELISA)
- At any time after vaccination the proportion of participants with  $\geq 8$  dmLT-specific IgA or IgG ASC /  $10^6$  peripheral blood mononuclear cells (PBMC) as measured by Enzyme-Linked ImmunoSpot Assay (ELISpot)
- At any time after vaccination, the proportion of participants with  $\geq 2$ -fold rise in ALS anti-dmLT-specific IgG and IgA titers over baseline measured by ELISA
- At any time after vaccination, the proportion of participants with a  $\geq 4$ -fold rise over baseline in dmLT-specific fecal IgA titers measured by ELISA
- At any time after vaccination, the proportion of participants with a  $\geq 4$ -fold rise over baseline in dmLT-specific salivary IgA titers measured by ELISA

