- A life-threatening adverse event, defined as an adverse event the occurrence of which, in the view of either the site principal investigator or sponsor, places the participant at immediate risk of death. It does not include an adverse event that, had it occurred in a more severe form, might have caused death.
- Inpatient hospitalization (defined by local practice as the study participant being present in the hospital greater than 24 hours) or prolongation of existing hospitalization,
- A persistent or significant incapacity or substantial disruption of the ability to conduct normal life functions, or
- A congenital anomaly/birth defect.
- Important medical events that may not result in death, be life-threatening, or require hospitalizations may be considered serious when, based upon appropriate medical judgment they may jeopardize the patient or participant and may require medical or surgical intervention to prevent one of the outcomes listed in this definition. Examples of such medical events include allergic bronchospasm requiring intensive treatment in an emergency room or at home, blood dyscrasias or convulsions that do not result in inpatient hospitalization, or the development of drug dependency or drug abuse.

Serum dmLT-specific Ig response is defined as a  $\geq 4$ -fold rise in dmLT-specific serum

Ig titers over baseline.

ASC dmLT-specific Ig response is defined as  $\geq 8$  dmLT-specific Ig ASC / $10^6$  PBMC.

Serum dmLT-specific toxin neutralization response is defined as a  $\geq 4$ -fold rise over baseline in toxin neutralization titers.

ALS response is defined as a  $\geq 2$ -fold rise in ALS anti-dmLT-specific Ig titers over baseline.

Salivary response is defined as a  $\geq 4$ -fold rise over baseline in dmLT-specific salivary IgA titers.

Fecal response is defined as a  $\geq 4$ -fold rise over baseline in dmLT-specific fecal IgA titers.

ASC Homing response is defined as the presence of dmLT-specific circulating ASC expressing gut homing receptors (integrin  $\alpha 4\beta 7$  in the absence or presence of CD62L).

B memory response is defined as a  $\geq 0.05\%$  increase from baseline in the percentage of antigen-specific Ig /total Ig B memory cells.

T cell response is defined as an increase of  $>0.05\%$  from baseline cell percentage.

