#### dmLT-specific IgA ASC by ELISpot

The number and percentage of participants showing with  $\geq 8$  dmLT-specific IgA ASC /  $10^6$  PBMC as measured by ELISpot will be presented with exact (Clopper-Pearson) two-sided 95% CI by treatment arm at Days 1, 8, 15, 22, 29, 36, and any time for Oral and Sublingual Cohorts and at Days 1, 8, 22, 29, 43, 50, and any time for Intradermal Cohorts (Table 49 and Table 50).

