#### dmLT-specific IgG ASC by ELISpot

The number and percentage of participants showing with  $\geq 8$  dmLT-specific IgG ASC /  $10^6$  PBMC as measured by ELISpot will be presented with exact (Clopper-Pearson) two-sided 95% CI by treatment arm at

Days 1, 8, 15, 22, 29, 36, and any time for Oral and Sublingual Cohorts and at Days 1, 8, 22, 29, 43, 50, and any time for Intradermal Cohorts ([Table 51](#) and [Table 52](#)).

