**Table 49: ASC IgA Response Results by Time Point and Treatment Group, mITT Population**

Time Point	Statistic	Cohort A: Oral 5 µg dmLT (N=X)	Cohort B: Oral 25 µg dmLT (N=X)	All Oral Cohorts: Placebo (N=X)	Cohort C: Sublingual 5 µg dmLT (N=X)	Cohort D: Sublingual 25 µg dmLT (N=X)	All Sublingual Cohorts: Placebo (N=X)	Cohort E: Intradermal 0.3 µg dmLT (N=X)	Cohort E: Intradermal Placebo (N=X)
Pre-Dose 1a	n	x	x	x	x	x	x	x	x
	Proportion with ASC Response g	x.xx	x.xx	x.xx	x.xx	x.xx	x.xx	x.xx	x.xx
	95% CI	x.xx, x.xx	x.xx, x.xx	x.xx, x.xx	x.xx, x.xx	x.xx, x.xx	x.xx, x.xx	x.xx, x.xx	x.xx, x.xx
Post-Dose 1 Day 7b	n								
	Proportion with ASC Response g								
	95% CI								
Pre-Dose 2c	n								
	Proportion with ASC Response g								
	95% CI								
Post-Dose 2 Day 7d	n								
	Proportion with ASC Response g								
	95% CI								
Pre-Dose 3e	n								
	Proportion with ASC Response g								
	95% CI								
Post-Dose 3 Day 7f	n								
	Proportion with ASC Response g								
	95% CI								
Any Time	n								
	Proportion with ASC Response g								
	95% CI								

Time Point	Statistic	Cohort A: Oral 5 µg dmLT (N=X)	Cohort B: Oral 25 µg dmLT (N=X)	All Oral Cohorts: Placebo (N=X)	Cohort C: Sublingual 5 µg dmLT (N=X)	Cohort D: Sublingual 25 µg dmLT (N=X)	All Sublingual Cohorts: Placebo (N=X)	Cohort E: Intradermal 0.3 µg dmLT (N=X)	Cohort E: Intradermal Placebo (N=X)
------------	-----------	---	--	--	---	--	--	--	--

N=Number of subjects in the mITT Population

a Day 1b Day 8c Day 15 for Oral & Sublingual Cohorts; Day 22 for Intradermal Cohortd Day 22 for Oral & Sublingual Cohorts; Day 29 for Intradermal Cohorte Day 29 for Oral & Sublingual Cohorts; Day 43 for Intradermal Cohortf Day 36 for Oral & Sublingual Cohorts; Day 50 for Intradermal Cohortg Defined as  $\geq 8$  IgA ASC/ $10^6$  PBMCs

Tables with similar format:

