**Table 50: ASC IgA Response Results by Time Point and Treatment Group, Oral & Sublingual Cohorts, Per Protocol Population**

**Table 51: ASC IgG Response Results by Time Point and Treatment Group, mITT Population**

Time Point	Statistic	Cohort A: Oral 5 µg dmLT (N=X)	Cohort B: Oral 25 µg dmLT (N=X)	All Oral Cohorts: Placebo (N=X)	Cohort C: Sublingual 5 µg dmLT (N=X)	Cohort D: Sublingual 25 µg dmLT (N=X)	All Sublingual Cohorts: Placebo (N=X)	Cohort E: Intradermal 0.3 µg dmLT (N=X)	Cohort E: Intradermal Placebo (N=X)
Pre-Dose 1a	n	x	x	x	x	x	x	x	x
	Proportion with ASC Response g	x.xx	x.xx	x.xx	x.xx	x.xx	x.xx	x.xx	x.xx
	95% CI	x.xx, x.xx	x.xx, x.xx	x.xx, x.xx	x.xx, x.xx	x.xx, x.xx	x.xx, x.xx	x.xx, x.xx	x.xx, x.xx
Post-Dose 1 Day 7b	n								
	Proportion with ASC Response g								
	95% CI								
Pre-Dose 2c	n								
	Proportion with ASC Response g								
	95% CI								
Post-Dose 2 Day 7d	n								
	Proportion with ASC Response g								
	95% CI								
Pre-Dose 3e	n								
	Proportion with ASC Response g								
	95% CI								
Post-Dose 3 Day 7f	n								
	Proportion with ASC Response g								
	95% CI								
Any Time Post Dose 1	n								
	Proportion with ASC Response g								
	95% CI								

Time Point	Statistic	Cohort A: Oral 5 µg dmLT (N=X)	Cohort B: Oral 25 µg dmLT (N=X)	All Oral Cohorts: Placebo (N=X)	Cohort C: Sublingual 5 µg dmLT (N=X)	Cohort D: Sublingual 25 µg dmLT (N=X)	All Sublingual Cohorts: Placebo (N=X)	Cohort E: Intradermal 0.3 µg dmLT (N=X)	Cohort E: Intradermal Placebo (N=X)
------------	-----------	---	--	--	---	--	--	--	--

N=Number of subjects in the mITT Population

a Day 1b Day 8c Day 15 for Oral & Sublingual Cohorts; Day 22 for Intradermal Cohortd Day 22 for Oral & Sublingual Cohorts; Day 29 for Intradermal Cohorte Day 29 for Oral & Sublingual Cohorts; Day 43 for Intradermal Cohortf Day 36 for Oral & Sublingual Cohorts; Day 50 for Intradermal Cohortg Defined as  $\geq 8$  IgA ASC/ $10^6$  PBMCs

Tables with similar format:

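### SAP 8.2 and Table 49 leave the any-time ASC summary open to the pre-dose Day 1 sample, against the endpoint's post-vaccination window; separately, the protocol and SAP cut-offs differ

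*SAP*

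**What the plan says.** **Endpoint.** Protocol 3.2.2 reads "At any time after vaccination the proportion of participants with > 8 dmLT-specific IgA or IgG ASC" per million PBMC. SAP 3.2.2 reads "At any time after vaccination the proportion of participants with $\geq 8$ dmLT-specific IgA or IgG ASC". Both set a post-vaccination window. They differ in the cut-off.

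**Responder rule.** SAP 3.3 states "ASC dmLT-specific Ig response is defined as $\geq 8$ dmLT-specific Ig ASC" per million PBMC. No rise over baseline is required.

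**Analysis text.** SAP 8.2 presents the IgA proportion "by treatment arm at Days 1, 8, 15, 22, 29, 36, and any time for Oral and Sublingual Cohorts", and the IgG proportion at "Days 1, 8, 15, 22, 29, 36, and any time for Oral and Sublingual Cohorts". The intradermal cohort has the same structure on its own visit days. The serum, ALS, fecal and salivary analyses in 8.2 start at Day 8, and their any-time summary is expressly limited to the period after the first dose.

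**Shells.** "Table 49: ASC IgA Response Results by Time Point and Treatment Group, mITT Population" has a pre-dose response row and, at the foot, an unqualified any-time row. The IgG counterpart, Table 51, also has a pre-dose row, but its summary row is labelled "Any Time Post Dose 1". The Table 51 footnote defines the IgG response in terms of IgA ASC.

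**Change log.** SAP Section 15 records the added safety laboratory tests and the COVID-19 disruption. It has no entry on the ASC cut-off.

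**The concern.** The endpoint definition and the specification a programmer would work from do not agree on the window. SAP 8.2 and Table 49 list Day 1 among the time points and then ask for a summary over any time. Table 51 asks for the summary after dose 1. Followed literally, the two shells would take in Day 1 for IgA and leave it out for IgG.

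This matters for ASC because the rule is an absolute count. With a fold-rise rule the baseline sample cannot be a response. With a fixed cut-off it can. Participants come from a community that protocol Section 4 describes as having much enteric disease. SAP 4.2 says the placebo recipients are there for blinding and not for comparison, so no planned contrast would remove background positivity.

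The cut-off is a second, independent matter. A threshold that differs between protocol and SAP without a record leaves it unclear which definition the reported proportion follows.

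**Working it through.** **1. Where can an unqualified any-time label let Day 1 in?**

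| Analysis | Day 1 sample? | Response rule (SAP 3.3) | Can Day 1 alone score? |
|---|---|---|---|
| Serum, ALS, fecal, salivary (8.2) | Yes, as baseline | Fold rise over baseline | No; window also limited to post-dose |
| Memory B cell (8.3) | Yes, listed | Increase from baseline | No |
| ASC homing (8.3) | None collected | Presence of homing ASC | No |
| ASC IgA (8.2, Table 49) | Yes, listed | Absolute count | Yes, read literally |
| ASC IgG (8.2, Table 51) | Yes, listed | Absolute count | Text: yes, read literally; shell: no |

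The conflict therefore has a practical consequence only for ASC. The text raises it for both isotypes, the shells only for IgA.

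**2. Effect of one participant positive only on Day 1.** The plan states no figure for the ASC endpoint. It specifies two-sided exact (Clopper-Pearson) intervals. As a check on that convention, SAP Section 5 gives an upper bound of 30.8% for 0/10, and 1 − 0.025^(1/10) = 30.85%.

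SAP 4.4.3 gives 12 dmLT and 3 placebo recipients per cohort.

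- dmLT arm: 1/12 = 8.3 points. For example, 6/12 = 50.0% (21.1% to 78.9%) becomes 7/12 = 58.3% (27.7% to 84.8%).
- Oral or sublingual placebo, pooled over two cohorts of 3: 1/6 = 16.7 points.

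**3. How many such participants?** The documents give no Day 1 positivity. For illustration only, let b be the share positive on Day 1 (assumed 5%, 10% or 20%) and p the share positive at some post-dose visit.

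- Chance of at least one Day 1 positive among 12, 1 − (1 − b)^12: 46%, 72%, 93%.
- Reported rate if Day 1 and post-dose positivity are independent, 1 − (1 − b)(1 − p); excess = b(1 − p):

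| p | b = 5% | b = 10% | b = 20% |
|---|---|---|---|
| 0% | 5% | 10% | 20% |
| 30% | 33.5% | 37% | 44% |
| 50% | 52.5% | 55% | 60% |

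Independence is an assumption too. If every Day 1 positive is also positive after a dose, the excess is zero. If none is, the excess is b, provided b + p does not exceed 100%. Only people positive on Day 1 and never afterwards change the count.

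**4. Cut-off.** >8 and ≥8 classify a participant differently only when the highest count in the window is exactly 8 per million PBMC. The documents give no distribution of counts, so the effect cannot be computed.

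**The case against.** The strongest reply is that the unqualified label is shorthand. SAP 3.2.2 keeps the post-vaccination window, and no sentence says that a Day 1 value feeds the summary. Showing Day 1 as its own row is not the same as pooling it. The IgG text has the same wording as the IgA text, yet its shell is limited to after dose 1. Memory B cell and homing analyses use the same loose label where Day 1 cannot count. All of this stands. It makes an unintended omission more likely than a deliberate rule, but it does not tell a programmer which text governs Table 49.

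It is also fair that the size is hypothetical. The exclusions for recent gastrointestinal symptoms, for moderate or severe diarrhea in the previous 6 weeks, for ETEC, *V. cholerae* or *Shigella* on screening culture, and for related vaccines within 3 years may keep Day 1 positivity low.

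The stakes are limited as well. No hypothesis is tested, and immunology data are not required for DSMB review. Table 49 shows each visit separately and Listing 9 gives individual counts, so a careful reader could see any Day 1 contribution.

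On the cut-off, a sign lost when the PDF was read cannot be fully excluded. However, the protocol shows > in both the Summary and 3.2.2, while neighbouring ≥ signs survived.

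**Conclusion.** The SAP contradicts itself and the protocol on the window for the ASC responder summary. Followed literally, SAP 8.2 and Table 49 would count a participant positive only before vaccination as an IgA responder, at 8.3 points per person in an arm of 12. The number of such participants is unknown, and the rates in the illustration rest on assumed Day 1 positivity and on independence. Separately, the cut-off differs by one boundary value and the change is unlogged; its effect cannot be computed.

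A reader might infer three stronger things that the documents do not support:

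- That the SAP has settled on counting pre-vaccination positives as responders, or on different rules for IgA and IgG. Its endpoint definition says otherwise, and the isotype difference rests on one row label.
- That the move to ≥8 causes pre-vaccination positives to count. It does not touch the window.
- That the protocol endpoint excludes Day 1 positives. It has no baseline condition, so someone positive on Day 1 who remains positive after dosing is a responder even under the correct window.

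This is a modest correction to a descriptive secondary endpoint. No safety or dose-escalation rule depends on it.

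**What to change.** - In SAP 8.2, for both IgA and IgG ASC, and in Tables 49 and 50, write *any time post first dose*. Confirm the same in Tables 51 and 52. Exclude Day 1 from the summary and keep it as a descriptive row.
- Use the protocol cut-off (>8), or record the change to ≥8 in Section 15 and show the proportion under both.
- Correct the Table 51 footnote so that it refers to IgG ASC.
- Optionally, as a supplementary display only, show the response among participants below the cut-off on Day 1, with that group as the stated denominator. This should not replace the protocol endpoint, because restricting to Day 1 negatives would be a new endpoint.

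The cost is SAP wording and shell edits, with no new data. Reported response rates would be the same or slightly lower.

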#### dmLT-specific IgG ASC by ELISpot

The number and percentage of participants showing with  $\geq 8$  dmLT-specific IgG ASC /  $10^6$  PBMC as measured by ELISpot will be presented with exact (Clopper-Pearson) two-sided 95% CI by treatment arm at

Days 1, 8, 15, 22, 29, 36, and any time for Oral and Sublingual Cohorts and at Days 1, 8, 22, 29, 43, 50, and any time for Intradermal Cohorts ([Table 51](#) and [Table 52](#)).

#### ALS anti-dmLT-specific IgA by ELISA

The number and percentage of participants showing  $\geq 2$ -fold rise from the baseline in ALS anti-dmLT-specific IgA titers determined by ELISA will be presented with exact (Clopper-Pearson) two-sided 95% CI by treatment arm at Days 8, 15, 22, 29, 36, and any time post first dose for Oral and Sublingual Cohorts and at Days 8, 22, 29, 43, 50, and any time post first dose for Intradermal Cohorts ([Table 53](#) and [Table 54](#)). Box and whisker plots of fold-rise over time will be presented ([Figure 76](#), [Figure 77](#), [Figure 78](#), [Figure 79](#), [Figure 80](#), and [Figure 81](#)).

#### ALS anti-dmLT-specific IgG by ELISA

The number and percentage of participants showing  $\geq 2$ -fold rise from the baseline in ALS anti-dmLT-specific IgG titers determined by ELISA will be presented with exact (Clopper-Pearson) two-sided 95% CI by treatment arm at Days 8, 15, 22, 29, 36, and any time post first dose for Oral and Sublingual Cohorts and at Days 8, 22, 29, 43, 50, and any time post first dose for Intradermal Cohorts ([Table 55](#) and [Table 56](#)). Box and whisker plots of fold-rise over time will be presented ([Figure 82](#), [Figure 83](#), [Figure 84](#), [Figure 85](#), [Figure 86](#), and [Figure 87](#)).

#### Fecal dmLT-specific IgA by ELISA

The number and percentage of participants showing  $\geq 4$ -fold rise from the baseline in dmLT-specific fecal IgA titers determined by ELISA will be presented with exact (Clopper-Pearson) two-sided 95% CI by treatment arm at Days 8, 15, 22, 29, 36, 57, and any time post first dose for Oral and Sublingual Cohorts and at Days 8, 22, 29, 43, 50, 71, and any time post first dose for Intradermal Cohorts ([Table 61](#), [Table 62](#), [Table 63](#), and [Table 64](#)). Box and whisker plots of fold-rise over time will be presented (beginning at [Figure 88](#) and concluding with [Figure 99](#)).

#### Salivary dmLT-specific IgA by ELISA

The number and percentage of participants showing  $\geq 4$ -fold rise from the baseline in dmLT-specific salivary IgA titers determined by ELISA will be presented with exact (Clopper-Pearson) two-sided 95% CI by treatment arm at Days 8, 15, 22, 29, 36, 57, and any time post first dose for Oral and Sublingual Cohorts and at Days 8, 22, 29, 43, 50, 71, and any time post first dose for Intradermal Cohorts ([Table 65](#), [Table 66](#), [Table 67](#), and [Table 68](#)). Box and whisker plots of fold-rise over time will be presented (beginning at [Figure 100](#) and concluding with [Figure 111](#)).

### 8.3. Exploratory Immunogenicity Analyses

#### ALS anti-dmLT-specific IgA by ELISA

Geometric mean titers and corresponding 95% confidence intervals of dmLT-specific IgA in ALS measured by ELISA will be presented by treatment arm at Days 1, 8, 15, 22, 29, and 36 for Oral and Sublingual Cohorts and at Days 1, 8, 22, 29, 43, and 50 for Intradermal Cohorts ([Table 31](#) and [Table 32](#)) will be presented. Box and whisker plots of log-titers over time will be presented ([Figure 22](#), [Figure 23](#), [Figure 24](#), [Figure 25](#), [Figure 26](#), and [Figure 27](#)).

#### ALS anti-dmLT-specific IgG by ELISA

Geometric mean titers and corresponding 95% confidence intervals of dmLT-specific IgG in ALS measured by ELISA will be presented by treatment arm at Days 1, 8, 15, 22, 29, and 36 for Oral and Sublingual Cohorts

and at Days 1, 8, 22, 29, 43, and 50 for Intradermal Cohorts ([Table 33](#) and [Table 34](#)) will be presented. Box and whisker plots of log-titers over time will be presented ([Figure 28](#), [Figure 29](#), [Figure 30](#), [Figure 31](#), [Figure 32](#), and [Figure 33](#)).

#### Serum dmLT-specific IgA by ELISA

Geometric mean titers and corresponding 95% confidence intervals of serum dmLT-specific IgA determined by ELISA will be presented by treatment arm at Days 1, 8, 15, 22, 29, 36, 57, and 114 for Oral and Sublingual Cohorts and at Days 1, 8, 22, 29, 43, 50, 71, and 128 for Intradermal Cohorts ([Table 21](#) and [Table 22](#)). Box and whisker plots of log-titers over time will be presented ([Figure 4](#), [Figure 5](#), [Figure 6](#), [Figure 7](#), [Figure 8](#), and [Figure 9](#)).

#### Serum dmLT-specific IgG by ELISA

Geometric mean titers and corresponding 95% confidence intervals of serum dmLT-specific IgG determined by ELISA will be presented by treatment arm at Days 1, 8, 15, 22, 29, 36, 57, and 114 for Oral and Sublingual Cohorts and at Days 1, 8, 22, 29, 43, 50, 71, and 128 for Intradermal Cohorts ([Table 23](#) and [Table 24](#)). Box and whisker plots of log-titers over time will be presented ([Figure 10](#), [Figure 11](#), [Figure 12](#), [Figure 13](#), [Figure 14](#), and [Figure 15](#)).

#### dmLT-specific IgA ASC by ELISpot

Mean and median number of dmLT-specific IgA ASC as measured by ELISpot will be presented by treatment arm at Days 1, 8, 15, 22, 29, and 36 for Oral and Sublingual Cohorts and at Days 1, 8, 22, 29, 43, and 50 for Intradermal Cohorts ([Table 27](#) and [Table 28](#)).

#### dmLT-specific IgG ASC by ELISpot

Mean and median number of dmLT-specific IgG ASC as measured by ELISpot will be presented by treatment arm at Days 1, 8, 15, 22, 29, and 36 for Oral and Sublingual Cohorts and at Days 1, 8, 22, 29, 43, and 50 for Intradermal Cohorts ([Table 29](#) and [Table 30](#)).

#### Fecal dmLT-specific IgA by ELISA

Geometric mean titers and corresponding 95% confidence intervals of dmLT-specific fecal IgA determined by ELISA will be presented by treatment arm at Days 1, 8, 15, 22, 29, 36, and 57 for Oral and Sublingual Cohorts and at Days 1, 8, 22, 29, 43, 50, and 71 for Intradermal Cohorts ([Table 35](#), [Table 36](#), [Table 37](#), and [Table 38](#)). Box and whisker plots of log-titers over time will be presented (beginning at [Figure 34](#) and concluding with [Figure 45](#)).

